6.5 Excluded Concomitant Medications and Procedures

The following medications and procedures are prohibited during the study:

Systemic treatment with any of the following metabolizing enzyme inhibitors is not permitted during this study. A DDI with a strong inhibitor would increase ixazomib exposure.

Strong inhibitors of CYP1A2: fluvoxamine, enoxacin, ciprofloxacin

Strong inhibitors of CYP3A: clarithromycin, telithromycin, itraconazole, voriconazole, ketoconazole, nefazodone, and posaconazole

Systemic treatment with any of the following metabolizing enzyme inducers should be avoided unless there is no appropriate alternative medication for the patient to use
(Rationale: Unlike with inhibitors, if there were to be a DDI with an inducer, ixazomib exposure would be less; therefore, there would be a reduced chance of an AE. However, there may be less chance for an antitumor effect, but that is not an absolute reason to be taken off Ixazomib):

Strong CYP3A inducers: rifampin, rifapentine, rifabutin, carbamazepine, phenytoin, and phenobarbital.

The dietary supplements St John's wort and Ginkgo biloba are not permitted.

The following procedures are prohibited during the study:

Any antineoplastic treatment with activity against RCC except for drugs in this treatment regimen.

Radiation therapy (the requirement for local radiation therapy generally indicates disease progression).

The following drugs are not permitted during the study: zidoudine, theophylline derivatives, telbivudine, ribavirin, pegloticase, methadone, fluoxetine, aldesleukin, clozapine.

Monitor closely any CYP2D6 or CYP2C9 substrate drugs as Pegylated IFN may decrease serum concentration of CYP2D6 substrates.

6.6 Permitted Concomitant Medications and Procedures

The following medications and procedures are permitted during the study:

- Antiemetics, including 5-HT3 serotonin receptor antagonists, may be used at the discretion of the investigator.
- Loperamide or other antidiarrheal should be used for symptomatic diarrhea at discretion of the investigator. The dose and regimen will be according to institutional guidelines. Intravenous fluids should be given as needed to prevent volume depletion.
- Growth factors (eg, granulocyte colony stimulating factor [G-CSF], granulocyte macrophage-colony stimulating factor [GM-CSF], recombinant erythropoietin) are

permitted. Their use should follow published guidelines and/or institutional practice; however, alternative usage may be reviewed with the PI. Erythropoietin will be allowed in this study. Its use should follow published guidelines and/or institutional practice.

- Patients should be transfused with red cells and platelets as clinically indicated and according to institutional guidelines.
- Antiviral therapy such as acyclovir may be administered if medically appropriate.
- Concomitant treatment with bisphosphonates and RANKL inhibitor denosumab will be permitted, as appropriate.
- Patients who experience worsening neuropathy from baseline may be observed for recovery and have dose reductions/delays as indicated in the protocol, and any supportive therapy or intervention may be initiated as appropriate at the discretion of the investigator.
- Supportive measures consistent with optimal patient care may be given throughout the study.

6.7 Precautions and Restrictions

Pregnancy

It is not known what effects ixazomib has on human pregnancy or development of the embryo or fetus. Therefore, female patients participating in this study should avoid becoming pregnant, and male patients should avoid impregnating a female partner. Nonsterilized female patients of reproductive age group and male patients should use effective methods of contraception through defined periods during and after study treatment as specified below.

Female patients must meet 1 of the following criteria:

Postmenopausal for at least 1 year before the screening visit, OR

Surgically sterile, OR

If they are of childbearing potential, agree to practice 2 effective methods of contraception, at the same time, from the time of signing the informed consent form through 90 days after the last dose of study drug, OR

Agree to practice true abstinence when this is in line with the preferred and usual lifestyle of the subject. (Periodic abstinence [eg, calendar, ovulation, symptothermal, post-ovulation methods] and withdrawal are not acceptable methods of contraception.)

Male patients, even if surgically sterilized (ie, status postvasectomy), must agree to 1 of the following:

- Agree to practice effective barrier contraception during the entire study treatment period and through 90 days after the last dose of study drug, OR
- Agree to practice true abstinence when this is in line with the preferred and usual lifestyle of the subject. (Periodic abstinence [eg, calendar, ovulation, symptothermal, post-ovulation methods] and withdrawal are not acceptable methods of contraception.)
- Pegylated IFN is a category C pregnancy risk and the above should be followed.

6.8 Preparation, Reconstitution, and Dispensing

Ixazomib

As with any anticancer drug caution should be exercised when handling ixazomib capsules.

Pegylated Interferon

Two B-D Safety Lok™ syringes are provided in the package; one syringe is for the reconstitution steps and one for the patient injection. There is a plastic safety sleeve to be pulled over the needle after use. The syringe locks with an audible click when the green stripe on the safety sleeve covers the red stripe on the needle. Brief instructions for the preparation and administration of PEG-Intron Powder for Injection are provided below. Please refer to the Medication Guide for detailed, step-by-step instructions.

Reconstitute the PEG-Intron lyophilized product with only 0.7 mL of supplied diluent (Sterile Water for Injection, USP). The diluent vial is for single use only. The remaining diluent should be discarded. No other medications should be added to solutions containing PEG-Intron, and PEG-Intron should not be reconstituted with other diluents. Swirl gently to hasten complete dissolution of the powder. The reconstituted solution should be clear and colorless. Visually inspect the solution for particulate matter and discoloration prior to administration. The solution should not be used if discolored or cloudy.

The reconstituted solution should be used immediately and cannot be stored for more than 24 hours at 2-80 C. The appropriate PEG-Intron dose should be withdrawn and injected subcutaneously. The PEG-Intron vial is a single use vial and does not contain a preservative. DO NOT REENTER VIAL. DISCARD UNUSED PORTION. Once the dose from a single dose vial has been withdrawn, the sterility of any remaining product can no longer be guaranteed. Pooling of unused portions of some medications has been linked to bacterial contamination and morbidity.

After preparation and administration of the PEG-Intron injection, it is essential to follow the procedure for proper disposal of syringes and needles. A puncture-resistant container should

be used for disposal of syringes. Patients should be instructed in the technique and importance of proper syringe disposal and be cautioned against reuse of these items (See MEDICATION GUIDE for detailed instructions.)

PEG-Intron is a white to off-white lyophilized powder supplied in 2-mL vials. The PEG-Intron Powder for Injection should be reconstituted with 0.7 mL of the supplied Diluent (Sterile Water for Injection, USP) prior to use. Below are the various vial sizes available and will be ordered based on a patient's weight in kg.

Each PEG-Intron Package Contains	
A box containing one 50 µg per 0.5 ml vial of PEG-Intron Powder for Injection and one 5 mL vial of Diluent (Sterile Water for Injection, USP), 2 B-D Safety Lok™ syringes with a safety sleeve and 2 alcohol swabs.	(NDC 0085-1368-01)
A box containing one 80 µg per 0.5 mL vial of PEG-Intron Powder for Injection and one 5 mL vial of Diluent (Sterile Water for Injection, USP), 2 B-D Safety Lok™ syringes with a safety sleeve and 2 alcohol swabs.	(NDC 0085-1291-01)
A box containing one 120 µg per 0.5 mL vial of PEG-Intron Powder for Injection and one 5 mL vial of Diluent (Sterile Water for Injection, USP), 2 B-D Safety Lok™ syringes with a safety sleeve and 2 alcohol swabs.	(NDC 0085-1304-01)
A box containing one 150 µg per 0.5 mL vial of PEG-Intron Powder for Injection and one 5 mL vial of Diluent (Sterile Water for Injection, USP), 2 B-D Safety Lok™ syringes with a safety sleeve and 2 alcohol swabs.	(NDC 0085-1279-01)

6.9 Packaging and Labeling

The study drug ixazomib capsules will be provided by Millennium. The study drug will be labeled and handled as open-label material, and packaging labels will fulfill all requirements specified by governing regulations.

Ixazomib capsules should be stored unopened at 2°C to 8°C (36°F-46°F). The capsules are individually packaged in cold form foil-foil blisters in a child-resistant package. The 0.2-, 0.5-, and 2.0 mg capsules are in 1 × 4 blister strips that are individually perforated. The strips (1 × 4) are placed in cartons containing 6 strips (24 total capsules) of the same

strength. The 2.3-, 3.0-, and 4.0 mg capsules are supplied as a 1 x 3 blister card in a child-resistant cardboard wallet.

PEG-Intron, should be stored at 25°C (77°F): excursions permitted to 15-30°C (59-86°F) [see USP Controlled Room Temperature]. After reconstitution with supplied Diluent the solution should be used immediately, but may be stored up to 24 hours at 2° to 8°C (36° to 46°F). The reconstituted solution contains no preservative, is clear and colorless. Do not freeze.

6.10 Storage, Handling, and Accountability

Upon receipt at the investigative site, ixazomib should remain in the blister and carton provided until use or until drug is dispensed. The container should be stored at the investigative site refrigerated (36°F to 46°F, 2°C to 8°C). Ensure that the drug is used before the retest expiry date provided by Millennium. Expiry extensions will be communicated accordingly with updated documentation to support the extended shelf life.

In countries where local regulations permit, ixazomib capsules dispensed to the patient for take-home dosing should remain in the blister packaging and refrigerated as noted above until the point of use. The investigative site is responsible for providing the medication to the patient in the correct daily dose configurations. Comprehensive instructions should be provided to the patient in order to ensure compliance with dosing procedures. Patients who are receiving take-home medication should be given only 1 cycle of medication at a time. Patients should be instructed to store the medication refrigerated (36°F to 46°F, 2°C to 8°C) for the duration of each cycle. Patients should be instructed to return their empty blister packs to the investigative site, rather than discarding them. Reconciliation will occur accordingly when the patient returns for their next cycle of take-home medication. Any extreme in temperature should be reported as an excursion and should be dealt with on a case-by-case basis.

Because ixazomib is an investigational agent, it should be handled with due care. Patients should be instructed not to chew, break, or open capsules. In case of contact with broken capsules, raising dust should be avoided during the clean-up operation. The product may be harmful by inhalation, ingestion, or skin absorption. Gloves and protective clothing should be worn during cleanup and return of broken capsules and powder to minimize skin contact.

The area should be ventilated and the site washed with soap and water after material pick-up is complete. The material should be disposed of as hazardous medical waste in compliance with federal, state, and local regulations.

In case of contact with the powder (eg, from a broken capsule), skin should be washed immediately with soap and copious amounts of water for at least 15 minutes. In case of contact with the eyes, copious amounts of water should be used to flush the eyes for at least 15 minutes. Medical personnel should be notified. Patients are to be instructed on proper storage, accountability, and administration of ixazomib, including that ixazomib is to be taken as intact capsules.

See above for handing, storage and administration of IFN.

6.11 Study Compliance

Study drug will be administered or dispensed only to eligible patients under the supervision of the investigator or identified sub-investigator(s). The appropriate study personnel will maintain records of study drug receipt and dispensing.

6.12 Treatment Assignment

All patients will be assigned combination treatment. In phase I this will be based on the cohort and in phase II it will be a set dose based on phase I. Dose modifications are permitted as described in section 6.2.

6.13 Termination of Treatment and/or Study Participation

In the absence of treatment delays due to adverse events, treatment may continue for unlimited cycles or until one of the following criteria applies:

- Disease progression
- Intercurrent illness that prevents further administration of treatment,
- Unacceptable adverse event(s)
- Patient decides to withdraw from the study
- General or specific changes in the patient's condition render the patient unacceptable for further treatment in the judgment of the investigator.
- Withdrawl of trial support by the Sponsor

Patients will be informed that they have the right to withdraw from the study at any time for any reason, without prejudice to their medical care.

Patients who are withdrawn from the study will not be replaced.

Treatment delay of \geq 21 days for any hematologic or non-hematologic toxicity will lead to permanent treatment discontinuation.

At the time of withdrawal, all study procedures outlined for the End of Study visit should be completed. The primary reason for patient's withdrawal from the study should be recorded in the source documents and CRF.

6.14 Long Term Follow Up

In regard to long-term follow-up, unless there is progression or withdrawal of consent, study follow-up will continue until 5 years maximum. Upon progression, patient will continue to be followed up for three years maximum with phone calls from the study coordinator every 3 months.

7 ADVERSE EVENTS

7.1 Definitions

7.1.1 Adverse Event Definition

Adverse event (AE) means any untoward medical occurrence in a patient or subject administered a pharmaceutical product; the untoward medical occurrence does not necessarily have a causal relationship with this treatment. An AE can therefore be any unfavorable and unintended sign (including an abnormal laboratory finding), symptom, or disease temporally associated with the use of a medicinal (investigational) product whether or not it is related to the medicinal product. This includes any newly occurring event, or a previous condition that has increased in severity or frequency since the administration of study drug.

An abnormal laboratory value will not be assessed as an AE unless that value leads to discontinuation or delay in treatment, dose modification, therapeutic intervention, or is considered by the investigator to be a clinically significant change from baseline.

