4.1.1 Definition of Dose Limiting Toxicity

Dose-limiting toxicity (DLT) is any drug related toxicity occurring during the first 28 days on study (cycle 1) that meets the parameters defined in Table 4-3.

Table 4-3. Dose Limiting Toxicity

Any grade 3 or 4 treatment related non-hematologic toxicity regardless of duration, except :

 Grade 3 nausea or Grade 3 vomiting \leq 72 hours that recovers to grade 0-2 with maximal antiemetic therapy. Grade 3 diarrhea that resolves to grade 0-2 with loperamide or diphenoxylate/atropine within 48 hours. Grade 3 hypercholesterolemia, hypertriglyceridemia, hyperglycemia or hypophosphatemia that resolves to grade 0-2 with medical management. Transient electrolyte abnormalities lasting \leq 1 week.
Grade 3 or 4 thrombocytopenia.
Grade 4 neutropenia associated with fever or hospitalization for infection.
Grade 4 neutropenia lasting longer than 5 days.
Any toxicity felt to be possibly or probably related to study medication that causes the patient to miss more than 1 dose of either Ixazomib or pIFN in the first 28 days.
Any unacceptable toxicity (UT) as defined for phase II below (Section 4.5)

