4.5 Definition of Unacceptable Toxicity

For this study we will have a category defined as unacceptable toxicity (UT). This will be used in the statistical design of the phase II part of the study and incorporated into an early stopping rule (see Figure 7-1). If a patient develops UT at any point in the study, he or she will be withdrawn from the study. If more than 1 UT occurs during the final 6 patients of Phase I of the study, the study will be halted for assessment and possible amendment (Figure 7-1).

UT is defined as any grade 5 toxicity, grade 4 neuropsychiatric toxicity or grade 4 clinically significant non-hematologic toxicity thought to be definitely, probably or possibly related to study drug.

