Neutropenia has been reported with ixazomib. Blood counts should be monitored regularly as outlined in the protocol with additional testing obtained according to standard clinical practice. Neutropenia may be severe but has been manageable with G-CSF according to standard clinical practice. Neutropenic nadirs commonly recover without intervention by the beginning of the next scheduled cycle or with a short delay in treatment. Ixazomib administration should be modified when neutropenia occurs, as noted in the dose modification recommendations in Table 6-2. Therapy can be reinitiated at a reduced level upon recovery of absolute neutrophil counts.

Fluid Deficits

Dehydration should be avoided because ixazomib may cause vomiting, diarrhea, and dehydration. Acute renal failure has been reported with ixazomib. Fluid deficits should be corrected before initiation of study drug and during treatment and as needed during therapy. Until further information is available, intake of NSAIDs while on this protocol should be avoided.

Hypotension

Symptomatic hypotension and orthostatic hypotension with or without syncope have been reported with ixazomib. Blood pressure should be closely monitored while the patient is on study treatment and fluid deficit should be corrected as needed, especially in the setting of concomitant symptoms such as nausea, vomiting, diarrhea, or anorexia. Patients taking medications and/or diuretics to manage their blood pressure (for either hypo- or hypertension) should be managed according to standard clinical practice, including considerations for dose adjustments of their concomitant medications during the course of the trial.

Posterior Reversible Encephalopathy Syndrome

One case of posterior reversible encephalopathy syndrome (PRES) has been reported with ixazomib. While this case ultimately resolved, PRES has also been reported rarely with another proteasome inhibitor, VELCADE. PRES is characterized by headache, seizures and visual loss, as well as abrupt increase in blood pressure. Prompt diagnosis and initiation of antihypertensive and anticonvulsant therapy are important to prevent irreversible end-organ damage.

Transverse Myelitis

Transverse myelitis has also been reported with ixazomib. It is not known if ixazomib causes transverse myelitis; however, because it happened to a patient receiving ixazomib, the possibility that ixazomib may have contributed to transverse myelitis cannot be excluded.

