7.2 Procedures for Reporting Serious Adverse Events

AEs may be spontaneously reported by the patient and/or in response to an open question from study personnel or revealed by observation, physical examination, or other diagnostic procedures. Any clinically relevant deterioration in laboratory assessments or other clinical finding is considered an AE. When possible, signs and symptoms indicating a common underlying pathology should be noted as one comprehensive event. For serious AEs, the investigator must determine both the intensity of the event and the relationship of the event to study drug administration. For serious pretreatment events, the investigator must determine both the intensity of the event and the relationship of the event to study procedures.

AEs which are serious must be reported to Millennium Pharmacovigilance (or designee) from the date the participant signs Informed Consent through 30 days after administration of the last dose of Ixazomib. Any SAE that occurs at any time after completion of Ixazomib treatment or after the designated follow-up period that the sponsor-investigator and/or sub-investigator considers to be related to any study drug must be reported to Millennium Pharmacovigilance (or designee). In addition, new primary malignancies that occur during the follow-up periods must be reported, regardless of causality to study regimen, for a minimum of three years after the last dose of the investigational product, starting from the first dose of study drug. All new cases of primary malignancy must be reported to Millennium Pharmacovigilance (or designee).

Planned hospital admissions or surgical procedures for an illness or disease that existed before the patient was enrolled in the trial are not to be considered AEs unless the condition deteriorated in an unexpected manner during the trial (e.g., surgery was performed earlier or later than planned). All SAEs should be monitored until they are resolved or are clearly determined to be due to a patient's stable or chronic condition or intercurrent illness(es).

7.2.1 Site reporting responsibilities:

Since this is an investigator-initiated study, the principal investigator [name], also referred to as the sponsor-investigator, is responsible for reporting serious adverse events (SAEs) to any regulatory agency and to the sponsor- investigator's EC or IRB.

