8.1.1 Definition of Phase II and exploratory endpoints and Analytic Plan

The phase II dose will be determined by an initial standard '3+3' phase I component as described in Section 4.1. Once a RP2D is reached, the phase II will begin.

Definition of phase II primary endpoint: Progression free survival at 8 and 16 weeks using RECIST v 1.1, defined from date of treatment initiation to date of progression according to RECIST or death, or is censored at the date of the last imaging. If patient is not evaluated at 8 and/or 16 weeks then the patient is not considered as alive and progression-free.

Definition of secondary outcomes/endpoints:

1. Composite of unacceptable toxicity at 8 weeks (grade 4 non-hematologic toxicity thought to be definitely, probably or possibly related to study drug)
2. Overall response using RECIST v1.1.

Definition of exploratory objectives:

1. Changes in STAT1 phosphorylation and MHC1 up regulation in PBMCs from baseline to week 2, 3, 7, EOT.
2. Degree of desmoplasia in archived FFPE tumor samples and change in serum IL-6
3. Degree of nuclear NF- κ B p65 and STAT1 in archived FFPE tumor samples

Analytic plan for primary and secondary objectives:

Kaplan Meier curves will be used to estimate the distribution of progression free survival, median survival, and 1-year survival. Proportions, 95% confidence intervals, will be used to characterize composite rate of unacceptable toxicity and overall response rate. All analyses are for estimation only, and no larger inference will be generated given the sample size of the study.

Analytic plan for exploratory objectives:

Pre- and post- treatment phosphorylation changes in pSTAT1 and MHC1 (flow data, the MFIs will be log10) and serum IL-6 will be analyzed by paired t-tests. Degree of desmoplasia and nuclear NF- κ B and STAT1 will be quantified using standard immunohistochemical methods. Statistical analysis for western blots and responders vs non-responders tumor immunohistochemistry will be performed using non-parametric Mann-Whitney test and/or paired t-tests.

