8.1.6 Safety Analysis

Safety analysis will be performed by the PI and biostatistics. Safety data will be reviewed by the Extramural Data Safety Monitoring Committee (EDMSC). Each patient will be monitored closely as detailed in the study calendar. Adverse events will be documented and summarized in table form. Interim analysis of toxicity, outcome and ongoing scientific investigations may be performed every 3 months by the Extramural Data Safety Monitoring Committee (EDSMC). In this capacity the EDSMC will serve as an advisory committee to ERP and FCCC IRB. The EDSMC will review those aspects of this trial that are outlined in the responsibilities section of the ERP Data and Safety Monitoring Plan (DSMP). If the committee decides that changes should be made to this trial, it will make recommendations in writing to the Extramural Research Committee and Division Medical Director and PI which, in turn, have the authority to approve or disapprove these recommendations. These changes will be discussed with the Study Principal Investigator before they are

implemented. These changes may include early termination of accrual. Other changes might include altering the accrual goals or changing the eligibility criteria for the trial.

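### Grade 3 neutropenia that recovers unaided, and uncomplicated grade 3-4 lymphopenia, may be left out of the safety results at the investigator's discretion, because laboratory values count as AEs only if acted on or judged significant and only AE tables are planned

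*Combined protocol and SAP*

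**What the plan says.** Section 7.1.1 sets the rule for laboratory data: "An abnormal laboratory value will not be assessed as an AE unless that value leads to discontinuation or delay in treatment, dose modification". The sentence goes on to admit values that lead to a therapeutic intervention, and any value that "is considered by the investigator to be a clinically significant change from baseline". No CTCAE grade makes a value an AE by itself.

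The safety analysis in Section 8.1.6 is brief: "Adverse events will be documented and summarized in table form". It also allows for review by the data safety monitoring committee. Section 8.1.1 adds one more toxicity analysis: "Proportions, 95% confidence intervals, will be used to characterize composite rate of unacceptable toxicity and overall response rate". Neither section plans a summary of laboratory values, although the Schedule of Events has a CBC with differential every week from week 2 to week 16.

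On how neutropenia behaves, Section 6.4 says: "Neutropenic nadirs commonly recover without intervention by the beginning of the next scheduled cycle". The same sentence adds recovery after a short treatment delay as an alternative.

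Two other places bear on the rule. Section 7.2 says: "Any clinically relevant deterioration in laboratory assessments or other clinical finding is considered an AE". Section 7.1.2 uses a grade 3 white cell count to illustrate an event that is severe but need not be serious.

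**The concern.** A safety table built only from AEs shows a laboratory toxicity only when it was recorded as an AE. Here that depends on whether someone acted on the value or judged it significant. A cytopenia that is severe by grade, resolves unaided and prompts no action can stay out of the table, and two investigators could record the same count differently.

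Both drugs are known to lower blood counts, and Section 6.4 itself links lymphopenia to infection and to herpes virus reactivation. Safety and tolerability of the combination are part of the phase I primary objective (Section 2). At stake is whether the reported rates of neutropenia and lymphopenia reflect the counts measured or the recording habits of the investigators.

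**Working it through.** **Step 1. Does another toxicity measure cover these events?**

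- *UT (Section 4.5)*: grade 5 events, grade 4 neuropsychiatric events and "grade 4 clinically significant non-hematologic toxicity thought to be definitely, probably or possibly related to study drug". Grade 3-4 cytopenia is not included.
- *DLT (Table 4-3)*: the neutropenia items are grade 4 with fever or hospitalization for infection, and "Grade 4 neutropenia lasting longer than 5 days". Lymphopenia is not listed. Related toxicity that causes more than one missed dose also counts, but missed doses would already make the value an AE.
- *Within-cycle hold (Table 6-2)*: starts at ANC at or below 0.50 x 10^9/L on an ixazomib dosing day.
- *Cycle start (Section 6.3)*: requires ANC of at least 1,000/mm3, which is 1.0 x 10^9/L.
- *Lymphocytes*: no rule in Sections 6.3 or 6.4 or Table 6-2 sets a lymphocyte threshold.

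An ANC above 0.50 and below 1.0 x 10^9/L in weeks 2-4, back to 1.0 by day 1, crosses neither ANC threshold. Calling this grade 3 assumes the CTCAE v4.0 cut-offs, which the protocol cites but does not reproduce. The lymphopenia point needs no cut-off, because no threshold exists.

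Thrombocytopenia is largely covered: grade 3-4 is a DLT, and platelets at or below 75 x 10^9/L on a dosing day trigger a hold.

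**Step 2. Reproduce the background rates.**

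Drug-related events with oral ixazomib, N = 384 (Table 1-9):

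| Event | Count | Computed | Printed |
|---|---|---|---|
| Neutropenia, grade 3 | 46 | 46/384 = 11.98% | 12 |
| Neutropenia, grade 3 or higher | 49 | 49/384 = 12.76% | 13 |
| Lymphopenia, grade 3 | 21 | 21/384 = 5.47% | 5 |
| Lymphopenia, grade 3 or higher | 23 | 23/384 = 5.99% | 6 |

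Pegylated IFN in mRCC (Figure 1-5): grade 3 neutropenia 4 (13%) and grade 3 lymphopenia 4 (13%). The denominator is not printed. Of the values from 28 to 36, only n = 32 reproduces all the percentages in that figure, so the rate is taken as 4/32 = 12.5%.

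**Step 3. Expected cases in the phase II analysis set.**

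Section 8.1.2 analyses 34 patients (6 + 11 + 17). Assume that the single-agent rates hold for the combination. The expected count is N x p, and the chance of at least one case is 1 - (1 - p)^N.

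| Event and source rate | Expected in 34 | Chance of at least one |
|---|---|---|
| Grade 3 neutropenia, ixazomib | 34 x 46/384 = 4.07 | 0.987 |
| Grade 3 neutropenia, pIFN | 34 x 4/32 = 4.25 | 0.989 |
| Grade 3 lymphopenia, ixazomib | 34 x 21/384 = 1.86 | 0.852 |
| Grade 3 lymphopenia, pIFN | 34 x 4/32 = 4.25 | 0.989 |

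With the 31 patients named in Section 4.3, the expected counts are 3.71 to 3.88 for neutropenia and 1.70 to 3.88 for lymphopenia, which does not change the conclusion.

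These are expected events, not expected omissions. Only those that resolve with no listed action and no judgement of significance could be missed, and the documents do not give that share.

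**The case against.** The strongest reply is that much of this toxicity will reach the AE table anyway.

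- Section 6.4 mentions recovery after a short delay and management with G-CSF, and says that ixazomib should be modified when neutropenia occurs. Each of these makes the value an AE under 7.1.1.
- The Table 6-2 row on all hematologic toxicities deals with toxicity that recovers before the next cycle, and reduces ixazomib at that cycle when timing meant no reduction was required earlier.
- Antiviral therapy started for lymphopenia is an intervention.
- Section 7.2, the example in 7.1.2 and the opening paragraph of 7.1.1, which counts an abnormal laboratory finding among possible AEs, all lean toward reporting.

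This stands in part. It rules out saying that such counts never lead to action. It does not close the gap. The Table 6-2 row gives off-week timing as its case for a new reduction and states no count threshold, so it does not clearly reach an ANC of 0.5-1.0 in weeks 2-4. Antivirals are optional. Section 7.2 replaces one judgement (clinically significant) with another (clinically relevant), and the 7.1.2 example is only an illustration.

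Three stronger readings are tempting, and the documents do not support them:

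- *That the choice of RP2D is compromised.* Escalation uses the DLT list, and the phase II toxicity rule uses UT. Neither counts uncomplicated grade 3 neutropenia or lymphopenia, by design.
- *That the rates are understated.* They may be; the share that resolves without action is not given.
- *That comparison with the ixazomib data in Section 1 is impossible.* Those rates are themselves AE counts, recorded under rules not shown here, so comparability is uncertain. Rates taken from graded counts would not be directly comparable with them either.

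It is also fair to say that the raw counts are collected and that the monitoring committee may review toxicity. Neither commits the trial to reporting the graded values.

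**Conclusion.** The point holds as a reporting gap that should be closed. Whether uncomplicated grade 3 neutropenia in weeks 2-4 and uncomplicated grade 3-4 lymphopenia appear in the safety results rests on investigator judgement, although the counts are measured weekly. About 4 grade 3 neutropenia and 2 to 4 grade 3 lymphopenia cases are expected among 34 patients, so the rule will very probably matter for some patients; how many would be left out cannot be estimated.

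This rests on two assumptions: single-agent rates carry over to the combination, and CTCAE v4.0 grade 3 neutropenia is an ANC of 0.5 to below 1.0 x 10^9/L. Sample size, power and the DLT, RP2D and UT decision rules are unaffected. What is weakened is the description of safety and tolerability.

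**What to change.** 1. In Section 8.1.6, add a table of worst CTCAE v4.0 grade and shift from baseline for the scheduled hematology values (ANC, lymphocytes, platelets, hemoglobin), regardless of AE status. Present it for cycle 1 and overall, by dose level and for the phase II patients.
2. In Section 7.1.1, state that grade 3-4 hematologic values are recorded as AEs whatever action is taken.
3. Reconcile 7.1.1 with 7.1.2 and 7.2, so that one rule decides when a laboratory value is an AE.
4. Keep the AE table beside the laboratory table, because the historical ixazomib rates are AE-based and the graded-count rates will not be directly comparable with them.

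The cost is one extra table from data already scheduled for collection, some additional AE recording, and hematologic toxicity that may look less favourable. No dose or management rule changes.
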